- Change from baseline in number of binge days per week at Weeks 1, 2, 3, 4, 6, 8, and 10
- Change from baseline in number of binge episodes per week at Weeks 1, 2, 3, 4, 6, 8, 10, and 12
- Change from baseline in BE-CGI-S score at Weeks 2, 4, 6, 8, and 10
- Change from baseline in Y-BOCS-BE total score at Weeks 2, 4, 6, 8, and 10 and subscale scores (obsessions and compulsions) at Weeks 2, 4, 6, 8, 10, and 12
- Change from baseline in SDS total score and subscale scores (school/work disability, social life disability, and family life disability) at Weeks 6 and 12
- Change from baseline in MADRS total score at Week 12
- Change from baseline in HAM-A total score at Week 12
- Proportion of binge eating responders who have $\geq 75\%$ reduction in the number of binge eating episodes from Baseline at Week 12
- Change from baseline in EDE-Q modified including EDE-Q7 global score and 3 subscale scores (dietary restraint, shape/weight overvaluation, and body dissatisfaction) at Week 12

Safety Endpoints:

- The incidence of overall AEs, serious AEs (SAEs), and AEs (or SAEs) leading to discontinuations
- Clinical laboratory evaluations (serum chemistry, hematology, and urinalysis)
- Clinical evaluations (vital signs including orthostatic effects, and 12-lead ECGs)
- Frequency and severity of suicidal ideation and suicidal behavior as assessed by the C-SSRS
- Change and percent change from baseline in body weight at Weeks 1, 2, 3, 4, 6, 8, 10, and 12

- Change and percent change from baseline in BMI at Weeks 1, 2, 3, 4, 6, 8, 10, and 12
- Change from baseline in a fasting lipid panel (triglycerides, total cholesterol, high-density lipoprotein [HDL] cholesterol, and low-density lipoprotein [LDL] cholesterol) at Weeks 6 and 12
- Change from baseline in hemoglobin A1c level at Weeks 6 and 12
- Change from baseline in fasting glucose level at Weeks 6 and 12
- Change from baseline in insulin and high-sensitivity C-reactive protein (hs-CRP)
- Occurrence of symptoms of withdrawal from dasotraline measured by change from Week 12/EOT in:
 - CSSA total score at Weeks 13, 14, and 15
 - DESS total score at Weeks 13, 14, and 15
 - HAM-A total score at Weeks 13, 14, and 15
 - MADRS total score at Weeks 13, 14, and 15

Pharmacokinetic Endpoint:

Relationship between dasotraline plasma concentration and the primary endpoint in addition to selected secondary efficacy and safety endpoints

Statistical Methods:

Primary Efficacy Endpoint Analyses

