| 12-lead electrocardiogram (ECG) | X | X | | | | X | | X | | X | X | X | X |
| Columbia – Suicide Severity Rating Scale (C-SSRS) ⁿ | X | X | X | X | X | X | X | X | X | X | X | X | X |
| Adverse Events ^o | | | X | X | X | X | X | X | X | X | X | X | X |
| Serum chemistry | X | X | | | | | | X | | X | | | X |
| Lipid panel ^p | X | X | | | | | | X | | X | | | X |

Table 2: Schedule of Assessments (Continued)

| Procedures | Screening | Baseline | Treatment Period | | | | | | | | Withdrawal Period ^{a,b} | | |
|--|---------------|----------|------------------|--------------|--------------|--------------|--------------|--------------|--------------|--------------------------|----------------------------------|--------------|---------------|
| | V1 | V2 | V3 | V4 | V5 | V6 | V7 | V8 | V9 | V10 ^c | V11 | V12 | V13 |
| | | | Week 1 | Week 2 | Week 3 | Week 4 | Week 6 | Week 8 | Week 10 | Week 12/EOT ^a | Week 13 | Week 14 | Week 15 |
| | Day -22 to -2 | Day -1 | Day 7 (± 2) | Day 14 (± 2) | Day 21 (± 2) | Day 28 (± 2) | Day 42 (± 3) | Day 56 (± 3) | Day 70 (± 3) | Day 84 (± 1) | Day 91 (± 1) | Day 98 (± 1) | Day 105 (± 1) |
| Hemoglobin A1c | X | X | | | | | X | | | X | | | X |
| Insulin ^p | | X | | | | | | | | X | | | |
| hs-CRP | | X | | | | | | | | X | | | |
| Hematology | X | X | | | | | X | | | X | | | X |
| Urinalysis | X | X | | | | | X | | | X | | | X |
| Serum Pregnancy Test (in females of child-bearing potential) | X | | | | | | | | | | | | X |
| Urine Pregnancy Test (in females of child-bearing potential) | | X | | | | X | | X | | X | | | |
| Urine Drug Screen | X | X | | | | | X | | | X | X | X | X |
| Breath alcohol test | X | X | | | | | X | | | X | X | X | X |
| Blood sampling for plasma PK levels ^q | | | | X | | | X | | | X | | | |
| Blood sampling for potential biomarkers | | X | | | | | | | | X | | | |
| Blood sampling genotyping | | X | | | | | | | | | | | |

Footnotes are on the next page.

Abbreviations: CST = Clinical Surveillance Team; EOT = End of Treatment; hs-CRP = high-sensitivity C-reactive protein; PK = pharmacokinetic; V = visit

- ^a Subjects who discontinue from study drug before completion of the 12-week treatment period will be asked to return to the clinic and complete the End of Treatment visit as soon as possible following discontinuation of study drug and complete the 3-week withdrawal period.

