11. STUDY ASSESSMENTS

A study schematic is presented in [Figure 1](#). A summary of assessments to be conducted at each visit is presented in [Table 2](#).

Training, as appropriate, will be provided for study site staff administering each of the effectiveness and safety assessments. In an effort to improve the consistency of subject assessment across sites, an independent rater qualification service will provide training on the Mini International Neuropsychiatric Interview (MINI), SCID-I Module H, EDE-Q, EDE-Q modified, Y-BOCS-BE, BE-CGI-S, MADRS, SDS, HAM-A, CSSA, and DESS rating scales. In an effort to improve rater consistency and precision, an independent rater qualification service, in collaboration with the sponsor, will develop a credential and experience survey to identify raters with appropriate experience. The sponsor has final discretion regarding allowing raters to participate in the study.

Table 6 outlines the clinical assessments that will be conducted by site raters or self-report by subject. It is recommended that the assessments are conducted in the sequence noted in Table 6.

Table 6: Recommended Schedule for Clinical Assessments

| Screening Visit (Visit 1) | Baseline Visit (Visit 2) | Visits 3, 4, 5, 6, 7, 8, 9, 10, 11, 12, and 13 (as applicable, see Table 2 , schedule of assessments above and Section 11.8) |
|---------------------------|-----------------------------|---|
| SCID-I Module H | Review binge diary | Review binge diary |
| MINI | Y-BOCS-BE | Y-BOCS-BE |
| EDE-Q (by subject) | EDE-Q modified (by subject) | EDE-Q modified (by subject) |
| MADRS | SDS (by subject) | SDS (by subject) |
| C-SSRS | MADRS | MADRS |
| BE-CGI-S | C-SSRS | C-SSRS |
| Binge-diary training | BE-CGI-S | BE-CGI-S |
| | HAM-A | HAM-A |
| | | CSSA |
| | | DESS |

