- Record concomitant medications
- Collect vital signs and weight
- Perform ECG
- Record AEs
- Clinician review of binge eating diary and retraining, as necessary
- Administer scales:
 - Y-BOCS-BE
 - C-SSRS
 - BE-CGI-S
- Collect sample for urine pregnancy test for females of child-bearing potential
- Perform study medication accountability
- Dispense study medication
- Remind subject to fast for at least 8 hours (water and study drug only) prior to the Visit 7 Week 6 (Day 42) visit.

Subjects will complete the daily binge eating diary each day until the next clinic visit.

11.8.6. Week 6 (Day 42 [\pm 3 days]): Visit 7

The Week 6 visit should be scheduled in the morning. Subjects must be fasting for at least 8 hours (may have water and study drug only) prior to the indicated laboratory tests. The following study related procedures will be performed:

- Record concomitant medications
- Collect vital signs and weight
- Record AEs
- Clinician review of binge eating diary and retraining, as necessary
- Administer scales:
 - SDS
 - Y-BOCS-BE
 - C-SSRS
 - BE-CGI-S
- Collect sample for UDS
- Perform breath alcohol test
- Collect samples for hematology, serum chemistry, fasting lipid panel, hemoglobin A1c level, urinalysis
- Collect blood sample for plasma PK levels
- Perform study medication accountability
- Dispense study medication

Subjects will complete the daily binge eating diary each day until the next clinic visit.

11.8.7. Week 8 (Day 56 [± 3 days]): Visit 8

The following study related procedures will be performed:

- Record concomitant medications
- Collect vital signs and weight
- Perform ECG
- Record AEs
- Clinician review of binge eating diary and retraining, as necessary
- Administer scales:
 - Y-BOCS-BE
 - C-SSRS
 - BE-CGI-S
- Collect samples for urine pregnancy test for females of child-bearing potential
- Perform study medication accountability
- Dispense study medication

Subjects will complete the daily binge eating diary each day until the next clinic visit.

11.8.8. Week 10 (Day 70 [\pm 3 days]): Visit 9

The following study related procedures will be performed:

- Record concomitant medications
- Collect vital signs and weight
- Record AEs
- Clinician review of binge eating diary and retraining, as necessary
- Administer scales:
 - Y-BOCS-BE
 - C-SSRS
 - BE-CGI-S
- Perform study medication accountability
- Dispense study medication

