7.4.3.1 Treatment Period

Descriptive statistics (N, mean, standard deviation, median, and range) will be reported for each continuous laboratory analyte at baseline, each scheduled post-baseline time point, and endpoint for observed value as well as change from baseline. Categorical results (eg, urinalysis tests) will be summarized at each visit by treatment group using frequency and percentage. If a subject has more than one measurement at any time point, the one closest to the scheduled visit will be used in the by-visit analysis. All lab values will be presented in the data listings.

Results for glucose and lipid tests (HDL cholesterol, LDL cholesterol, total cholesterol, and triglycerides) will be presented separately by fasting status, which includes fasting only and overall (fasting, non-fasting, or unknown). The change from baseline value at endpoint for these selected laboratory parameters (ie, lipid tests, glucose, HbA1c, and insulin), will be evaluated using a nonparametric rank ANCOVA. For the comparison of each dasotraline group versus placebo group, the change from baseline at endpoint and baseline value is ranked. A linear regression will be conducted on the change from baseline ranks and baseline value rank as independent variable to produce regression residuals. Using the values of the residuals as scores, Mantel-Haenszel row mean score tests will be produced for each dasotraline group versus placebo group.

In addition, the change from baseline value at Weeks 6, 12, and endpoint for these selected laboratory parameters (ie, lipid tests, glucose, HbA1c, and insulin), will be further evaluated

321

using an ANCOVA model which includes terms for treatment, baseline binge days group, and the corresponding baseline as covariate. The LS means of treatment differences (each dasotraline group minus placebo group) and 2-sided 95% CIs will be obtained from the model.

The normal reference ranges for laboratory tests will be used to determine whether the laboratory test value is below, within, or above the normal range. Shifts from baseline to endpoint will be produced by treatment group to show the percentage of subjects with laboratory test values below, within, and above the normal range.

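### Table 2 schedules mid-treatment serum chemistry (including glucose) and lipids at Week 8, while the endpoints, visit instructions and SAP analyses place them at Week 6

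*Protocol*

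**What the plan says.** In the schedule of assessments (protocol Table 2) the two rows in question read "Serum chemistry | X | X | | | | | | X | | X | | | X" and "Lipid panel ^p | X | X | | | | | | X | | X | | | X". The HbA1c row in the same schedule reads "Hemoglobin A1c | X | X | | | | | X | | | X | | | X", with its mid-treatment mark one column earlier. Appendix II lists glucose among the blood chemistries, so the chemistry row governs glucose.

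The other texts agree with each other:

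- **Synopsis and Section 6.4** define the glucose endpoint as "Change from baseline in fasting glucose level at Weeks 6 and 12" and set the same weeks for the fasting lipid panel.
- **Section 11.8.5 (Week 4)** has the site remind subjects to fast "prior to the Visit 7 Week 6 (Day 42) visit".
- **Section 11.8.6 (Week 6)** instructs the site: "Collect samples for hematology, serum chemistry, fasting lipid panel, hemoglobin A1c level, urinalysis".
- **Section 11.8.7 (Week 8)** lists a urine pregnancy sample but neither chemistry nor lipids.
- **SAP 7.4.3.1** plans an ANCOVA of "the change from baseline value at Weeks 6, 12, and endpoint for these selected laboratory parameters", which include the lipid tests and glucose.

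No footnote to Table 2 explains the difference.

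**The concern.** Section 11 sends the reader to Table 2: "A summary of assessments to be conducted at each visit is presented in" that table. Site staff commonly work from such a schedule, and one that did so here would draw these two panels at Week 8 and not at Week 6. The protocol-defined Week 6 changes in fasting glucose and lipids, and the matching SAP summaries and ANCOVA, would then have no values from that site's continuing subjects.

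Fasting is a second, smaller issue. Section 11.8 ties the mid-treatment fasting reminder and the morning appointment to Week 6. At Week 8 the only fasting requirement is Table 2 footnote p, which is attached to the lipid row but not to the chemistry row. A glucose sample drawn at Week 8 might therefore not be a fasting one, and SAP 7.4.3.1 reports glucose and lipids by fasting status.

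**Working it through.** The plan gives no figure to reproduce. The check is a column count and a comparison of texts.

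**1. Column positions.** Table 2 has 13 visit columns; column 7 is Visit 7 (Week 6) and column 8 is Visit 8 (Week 8). Splitting the rows at the cell dividers gives:

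- Serum chemistry: 13 cells, marks at 1, 2, 8, 10, 13.
- Lipid panel: 13 cells, marks at 1, 2, 8, 10, 13.
- The Section 11.8 visit lists for both panels: 1, 2, 7, 10, 13.

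Only the mid-treatment mark differs.

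**2. Is the whole table shifted?** All 15 laboratory, ECG and sampling rows have 13 cells. The other 13 match the Section 11.8 lists:

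- ECG: 1, 2, 6, 8, 10–13
- HbA1c, hematology, urinalysis: 1, 2, 7, 10, 13
- Insulin, hs-CRP, biomarkers: 2, 10
- Serum pregnancy: 1, 13
- Urine pregnancy: 2, 6, 8, 10
- Urine drug screen, breath alcohol: 1, 2, 7, 10–13
- PK: 4, 7, 10
- Genotyping: 2

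In the two odd rows the marks at columns 10 and 13 are also where Section 11.8 puts them, so those rows are not displaced as a whole.

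**3. Could a Week 8 sample serve as Week 6?** The visit windows do not meet. Week 6 is 42 ± 3 = Days 39–45 and Week 8 is 56 ± 3 = Days 53–59. The gap runs from 53 − 45 = 8 days to 59 − 39 = 20 days. SAP 6.1.4.1 analyses data under the eCRF visit label and re-maps only early-termination visits. SAP 7.4.1 rules out imputing laboratory values in by-visit analyses. So a scheduled Week 8 sample stays at Week 8, and Week 6 stays empty for that subject.

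**4. Who would still have a Week 6 value at such a site?** SAP Table 4, which covers laboratory data, maps an early-termination visit to Week 6 when the last scheduled visit was Week 4. Section 11.8.9 collects both panels at that visit. The Week 4 window is 28 ± 2 = Days 26–30, so such a value could arise from 26 + 1 = Day 27. The site's Week 6 data would then come only from subjects who stopped early.

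**5. Scale.** The analytes are glucose, total cholesterol, LDL, HDL and triglycerides: five. The planned-region counts in SAP Table 6.3 sum to 59 + 75 + 50 + 69 + 55 + 22 + 88 + 70 + 3 = 491 subjects, and SAP 6.1.5.1 reports 50 sites. The average is 491 / 50 = 9.8 randomized subjects per site, about 2.0% of the total, before dropout. The documents do not say how many sites, if any, followed Table 2, so no trial-wide count can be given.

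**The case against.** **The misplaced marks may be a conversion fault.** The two rows are adjacent and sit at the end of a table block, just before a page break. A count of 13 cells does not prove that a mark is in the right cell. Among the laboratory, ECG and sampling rows, ECG is the only other one in that block, and so the only one there that tests Week 6 against Week 8; the remaining matching rows fall in the next block. This stands as a reason to look at the source PDF first. It does not make a fault likely: the ECG row parses correctly, and the same single mark would have to be displaced in both rows while their other marks stayed in place.

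**The operative instructions are clear.** Table 2 is only a summary, Section 11.8 is explicit, and SAP Section 3 points to Section 11.8 for visit detail. Even under Table 2, blood is drawn at Week 6 for HbA1c, hematology and PK. The central laboratory manual and the SAP's own copy of the schedule (Attachment 9.1) are not available to show what sites were told. This lowers the chance of harm but does not remove the contradiction.

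**A stronger reading is tempting.** A reader might infer that the SAP leaves Week 8 samples unaddressed, so that they could be counted as Week 6 unless a rule is added before database lock. SAP 6.1.4.1 does not support that: the eCRF label governs, only early-termination visits move, and unscheduled measurements are kept for the markedly abnormal and worst-case safety analyses. A reader might also infer that the Week 6 analyses are lost across the trial. Nothing in the documents shows that any site drew these panels at Week 8.

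**Timing.** SAP 6.1.7 refers to enrollment as complete, so a correction may change little data collection. That limits the practical gain.

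**Conclusion.** Table 2 contradicts the rest of the protocol and the SAP on when the mid-treatment serum chemistry and lipid panels are drawn, and Table 2 is the text that is wrong. For continuing subjects at any site that followed it, the Week 6 glucose and lipid analyses would have no values.

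The impact is minor. It concerns one mid-treatment safety time point, in analyses that SAP 7.4.1 declares descriptive, and one mid-treatment panel is drawn under either reading. Week 12, HbA1c and efficacy analyses are untouched, and the endpoint analysis is unchanged for every subject with a Week 12/EOT sample.

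The conclusion assumes that the source PDF shows the marks where the extracted text has them. The consequence further assumes that at least one site worked from Table 2 and not from Section 11.8; how many did is unknown.

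**What to change.** Check the source PDF of Table 2. If the marks are at Visit 8 there too, move them to Visit 7 in the serum chemistry and lipid panel rows and notify sites. Both rows would then read Visits 1, 2, 7, 10 and 13, as for HbA1c, hematology and urinalysis, and would agree with Sections 6.4 and 11.8.6 and SAP 7.4.3.1. If SAP Attachment 9.1 repeats the error, correct it there as well.

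No new SAP rule is needed to keep Week 8 samples out of Week 6, because SAP 6.1.4.1 already does so. The cost is two marks and a site memo, with no added visits or samples.

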3. LIST OF ABBREVIATIONS AND DEFINITIONS OF TERMS

The abbreviations and the definition of key study terms used in the clinical study protocol are shown in Table 3 and [Table 4](#).

Table 3: List of Abbreviations

| Abbreviation | Full Form |
|--------------|--|
| ADHD | Attention deficit hyperactivity disorder |
| ADHD-RS-IV | ADHD Rating Scale Version IV with adult prompts |
| AE | Adverse event |
| ALT | Alanine aminotransferase |
| ANCOVA | Analysis of covariance |
| APMP | Abuse Potential Monitoring Plan |
| AST | Aspartate aminotransferase |
| BE-CGI-S | Binge-eating Clinical Global Impression-Severity |
| BED | Binge eating disorder |
| BMI | Body mass index |
| BN | Bulimia nervosa |
| BUN | Blood urea nitrogen |
| CFR | Code of Federal Regulations |
| CI | Confidence interval |
| CR | Controlled release |
| CRF | Case report form |
| CRO | Clinical research organization |
| C-SSRS | Columbia-suicide severity rating scale |
| CSSA | Cocaine Selective Severity Assessment |
| CST | Clinical Surveillance Team |
| CTM | Clinical trial material |
| DA | Dopamine |
| DAT | Dopamine transporter |
| DB | Double blind |
| DBL | Database lock |
| DEAE | Discontinuation-emergent adverse event |
| DESS | Discontinuation-Emergent Signs and Symptoms |

Table 3: List of Abbreviations (Continued)

| Abbreviation | Full Form |
|---------------------|---|
| DHPG | 3,4-dihydroxyphenylglycol |
| DMP | Data Management Plan |
| DNA | Deoxyribonucleic acid |
| DNRI | Dopamine and norepinephrine reuptake inhibitor |
| DSM-5 | Diagnostic and Statistical Manual of Mental Disorders, 5th Edition |
| DSM-IV-TR | Diagnostic and Statistical Manual of Mental Disorders, 4th Edition Text Revised |
| DSMB | Data and Safety Monitoring |
| ECG | Electrocardiogram |
| EDC | Electronic data capture |
| EDE-Q | Eating Disorder Examination Questionnaire |
| EOT | End of treatment |
| ESAM | Event subject to additional monitoring |
| FDA | U.S. Food and Drug Administration |
| GCP | Good Clinical Practice |
| GEE | Generalized Estimating Equations |
| GLMM | Generalized linear mixed model |
| 5-HT | 5-hydroxytryptamine (serotonin) |
| HAM-A | Hamilton Anxiety Rating Scale |
| HDL | High-density lipoprotein (cholesterol) |
| HIV | Human immunodeficiency virus |
| HR | Heart rate |
| hs-CRP | High-sensitivity C-reactive protein |
| ICF | Informed consent form |
| ICH | International Conference on Harmonization |
| IEC | Independent Ethics Committee |
| IND | Investigational New Drug |
| IPW | Inverse probability weighting |
| IRB | Institutional Review Board |
| ITT | Intention-to-Treat |
| IUD | Intrauterine device |
| IXRS | Interactive Response System |

Table 3: List of Abbreviations (Continued)

| Abbreviation | Full Form |
|---------------------|--|
| LDL | Low-density lipoprotein (cholesterol) |
| LOCF | Last Observation Carried Forward |
| LS | Least squares |
| MADRS | Montgomery-Asberg Depression Rating Scale |
| MAO | Monoamine oxidase |
| MDD | Major Depressive Disorder |
| MedDRA | Medical Dictionary for Regulatory Activities |
| MHI | Medication Handling Irregularity |
| MINI | Mini International Neuropsychiatric Interview |
| MMRM | Mixed-effects Models Repeated Measures |
| MNAR | Missing not at random |
| MRI | Magnetic resonance imaging |
| NE | Norepinephrine |
| NET | Norepinephrine transporter |
| OTC | Over-the-counter (medications) |
| PCOS | Polycystic ovarian syndrome |
| PET | Positron emission tomography |
| PGx | Pharmacogenomics |
| PI | Principal Investigator |
| PK | Pharmacokinetic(s) |
| PP | Per-Protocol |
| PR | Time between P wave and QRS in electrocardiography |
| PT | Preferred term |
| QRS | Electrocardiographic wave (complex or interval) |
| QT | Electrocardiographic interval from the beginning of the QRS complex to the end of the T wave |
| QTc | QT interval corrected for heart rate |
| QTcB | corrected QT interval using Bazett's formula |
| QTcF | corrected QT interval using Fridericia's formula |
| RR | RR interval |
| SAE | Serious adverse event |
| SAP | Statistical analysis plan |

Table 3: List of Abbreviations (Continued)

| Abbreviation | Full Form |
|---------------------|---|
| SCID-I Module H | Structured Clinical Interview for DSM-IV Axis I Disorders, Module H |
| SD | Standard deviation |
| SDS | Sheehan Disability Scale |
| SERT | Serotonin transporter |
| SIGH-A | Structured Interview Guide for the HAM-A |
| SIGMA | Structured Interview Guide for the MADRS |
| SNRI | Serotonin norepinephrine reuptake inhibitor |
| SSRI | Selective serotonin reuptake inhibitor |
| SOC | System organ class |
| SOP | Standard operating procedure |
| t_{\max} | Time to maximum concentration |
| UDS | Urine drug screen |
| ULN | Upper limit of normal |
| USP | United States Pharmacopeia |
| VAS | Visual analog scale |
| WBC | White blood cells |
| WHO-DD | World Health Organization drug dictionary |
| Y-BOCS-BE | Yale-Brown Obsessive Compulsive Scale Modified for Binge Eating |

Table 4: Definition of Key Study Terms

| Terms | Definition of terms |
|----------------------------------|---|
| CRF | A printed, optical, or electronic document designed to record all of the protocol required information to report to the Sponsor for each study subject. |
| Study Drug (or Study medication) | Term to cover investigational drug, placebo, and/or active control. |
| Treatment Period | The period of the study in which the study drug is administered. |
| Randomized Subject | Any subject who was randomized into the treatment period of the study and is assigned a randomization number. |
| End of Treatment | The day that the subject receives protocol-defined last dose of the study drug. |

